3.8 Pharmacokinetic (PK) and Immunogenicity (IM) Analysis

Pharmacokinetic endpoints include the following:

- To evaluate the plasma trough levels of ISIS 420915 in all evaluable patients
- To evaluate the plasma pharmacokinetic parameters of ISIS 420915 in a subset of evaluable patients (PK subgroup).

Immunogenicity endpoints include the following:

- To evaluate sample IM status [confirmed positive, negative or unevaluable and, when applicable, titer of anti-ISIS 420915 antibodies (ADA)] before, during, and after treatment with ISIS 420915 or placebo in all evaluable patients

- To evaluate subject IM status (positive, negative or ‘unknown’) and its characteristics if applicable (onset, duration, peak titer, etc.)

Plasma samples will be collected at protocol designated times for ISIS 420915 plasma pharmacokinetic and immunogenicity assessments from patients receiving either ISIS 420915 300 mg or placebo treatment.

3.8.1 Plasma Pharmacokinetics

Pharmacokinetic analysis will be performed on two separation occasions: after all patients have completed treatment of ISIS 420915 (EOT) and at the end of the study (EOS).

3.8.1.1 Plasma Concentration Data

Plasma concentrations of ISIS 420915, along with the scheduled (nominal) and actual sampling times (i.e., time from SC dosing) will be listed for each evaluable patient by treatment, actual dose, gender, subject immunogenicity (IM) status, and study day. Plasma concentrations below the lower limit of quantification (LLOQ) will be indicated by “BLQ”. Percent differences between nominal and actual dose, as well as between scheduled and actual sampling times will also be listed for all patients.

For all patients who receive ISIS 420915 treatment, ISIS 420915 plasma trough and post-treatment concentrations will be summarized using descriptive statistics by dose, study day, and scheduled time point, without and with stratification by IM status (see Section 3.8.2). ISIS 420915 plasma concentrations from the PK subgroup will also be similarly summarized. For the purpose of calculating typical summary descriptive statistics (n, mean, standard deviation (SD), standard error (SE), %CV, geometric mean, geometric %CV, median, minimum, and maximum) for plasma concentrations, all BLQ values will be set to zero. Mean plasma concentrations that are below the LLOQ will be presented as BLQ, and the SD, SE, and %CV will be reported as not applicable. Other stratifications may also be performed if deemed warranted to properly interpret the pharmacokinetic analysis. Samples will be excluded from descriptive statistics if there are large deviations between scheduled and actual sampling times (percent difference between scheduled and actual sampling time greater than 30%), or large deviations between actual dose and nominal dose (percent difference between nominal and actual dose greater than 30%). Any samples excluded from the summary descriptive statistics, if deemed necessary, will be listed separately along with the reason for exclusion.

For all evaluable patients, ISIS 420915 plasma trough (predose) and post-treatment concentrations versus time (actual) profiles from Study Day 1 to 631 for each individual patient, as well as corresponding mean (\pm SD) plasma concentration versus time (scheduled) profiles will be presented graphically on linear and semilogarithmic scales, without and with stratification by subject immunogenicity status (see Section 3.8.2). For the PK subgroup only, ISIS 420915 plasma concentration versus time (actual) profiles from Study Day 1 to 3, from Study Day 240 to 247, and from Study Day 449 to 456, for each patient, as well as corresponding mean (\pm SD) plasma concentration versus time (scheduled) profiles (by treatment), will be presented graphically on

linear and semilogarithmic scales, without and with stratification by subject immunogenicity status (see Section 3.8.2). Other stratifications may also be performed if deemed warranted. At the discretion of the pharmacokineticist and/or biostatistician, samples may be excluded from the mean plots if there are large deviations between scheduled and actual sampling times, or large deviations between actual dose and nominal dose.

3.8.1.2 Plasma Pharmacokinetic Parameters

For ISIS 420915 treated patients only, non-compartmental pharmacokinetic analysis of ISIS 420915 will be carried out on each evaluable individual patient data using Phoenix WinNonlin version 6.3 or higher (Pharsight Corporation, Mountain View, CA) to determine plasma pharmacokinetic parameters. For calculation of PK parameters, all BLQ values will be set to zero.

For the PK subgroup (ISIS 420915 treated) only, the following plasma PK parameters will be calculated (when applicable and possible) based on actual sampling times:

- C_{max} ($\mu\text{g}/\text{mL}$): the maximum observed drug concentration in plasma. Calculated for dosing on Study Days 1, 240, and 449.
- T_{max} (hr): the time at which C_{max} occurs. Calculated for dosing on Study Days 1, 240, and 449.
- AUC_{0-24hr} ($\mu\text{g}\cdot\text{hr}/\text{mL}$): areas under the plasma concentration-time curve from zero time (pre-dose) to 24 hours after the SC administration will be calculated using the linear trapezoidal rule for dosing on Study Days 1, 240, and 449.
- AUC_{0-48hr} ($\mu\text{g}\cdot\text{hr}/\text{mL}$): areas under the plasma concentration-time curve from zero time (pre-dose) to 48 hours after the SC administration will be calculated using the linear trapezoidal rule for dosing on Study Day 1 only.
- AUC_{0-72hr} ($\mu\text{g}\cdot\text{hr}/\text{mL}$): areas under the plasma concentration-time curve from zero time (pre-dose) to 72 hours after the SC administration will be calculated using the linear trapezoidal rule for dosing on Study Days 240 and 449 only.
- $AUC_{0-168hr}$ ($AUC_{0-\tau}$) ($\mu\text{g}\cdot\text{hr}/\text{mL}$): partial AUC from time zero to 168 hr (dosing interval) will be calculated using the linear trapezoidal rule. This parameter will only be calculated for dosing on Study Days 240 and 449 only.
- MRT_{0-24hr} (hr): mean residence time (MRT) from time zero to 24 hours after the SC administration will be calculated from the equation, $MRT_{0-24hr} = AUMC_{0-24hr} / AUC_{0-24hr}$ where $AUMC_{0-24hr}$ is the area under the first moment plasma concentration-time curve from time zero to 24 hours after the SC administration. This parameter will be calculated for dosing on Study Day 1, 240, and 449. This parameter will be calculated and reported mainly as an index measure to reflect the expected initial rapid disposition of ISIS 420915 from plasma to tissues shortly after dosing.
- CL_{0-24hr} / F (L/hr): Plasma clearance will be calculated from $CL_{0-24hr} / F = \text{Actual Dose} / AUC_{0-24hr}$ for dosing on Study Day 1, 240, and 449.

- CL_{ss}/F (L/hr): Plasma clearance at steady-state will be calculated from $CL_{ss}/F = \text{Actual Dose}/AUC_{0-168hr}$ for dosing on Study Days 240 and 449 only.
- V_z/F (L): Apparent volume of distribution in the terminal phase will be calculated from $V_z/F = CL_{ss}/F/\lambda_z$ for dosing on Study Day 449 only. Note: calculation of this parameter may not be possible in any ISIS 420915 treated patients rolling into an open label extension study.

For all evaluable patients (including subjects participating in the PK subgroup) receiving active study drug (ISIS 420915), the following plasma PK parameters may be calculated (when applicable and determinable) based on actual sampling times at the discretion of the pharmacokineticist:

- $t_{1/2\lambda_z}$ (day): the plasma disposition half-life associated with the apparent terminal elimination phase may be calculated from the equation, $t_{1/2\lambda_z} = 0.693/\lambda_z$, based on any evaluable post-treatment data with scheduled collections on Days 491, 533, and 631. A minimum of three data points in the elimination phase will be used to define λ_z , and the correlation of determination values (r^2) have to be at or greater than 0.8 for the estimate to be accepted. Note: if quantifiable data is only available from just 2 time points or $r^2 < 0.8$, this parameter may still be determined at the discretion of the pharmacokineticist and will be flagged as such in the clinical study report. Note: calculation of this parameter may not be possible in any ISIS 420915 treated patients rolling into an open label extension study.
- $C_{\text{trough ave, Day 29-85}}$ (ng/mL): average plasma trough concentrations between Days 29 to 85 (Weeks 5 to 13).
- $C_{\text{trough ave, Day 155-240}}$ (ng/mL): average plasma trough concentrations between Days 155 to 240 (Weeks 23 to 35).
- $C_{\text{trough ave, Day 365-449}}$ (ng/mL): average plasma trough concentrations between Days 365 to 449 (Weeks 53 to 65).

Plasma pharmacokinetic parameters will be listed by dose, subject ID, gender, subject IM status, and study day; and appropriately summarized (separately for the PK subgroup and all evaluable ISIS 420915 treated patients) using descriptive statistics (n, mean, SD, SE, %CV, geometric mean, geometric %CV, median, minimum, and maximum) by study day. Additionally, subject IM status stratified (see Section 3.8.2) plasma pharmacokinetic parameters will be similarly summarized (again separately for the PK Subgroup and all evaluable ISIS 420915 treated patients). Other stratifications may also be performed if deemed warranted at the discretion of the pharmacokineticist and/or biostatistician.

Exposure-response relationships between selected pharmacodynamic (including but not limited to TTR level, mNIS+7 and Norfolk QOL-DN score) and pharmacokinetic measures (including but not limited to plasma trough concentrations) may also be explored (including with and without stratification by IM status), where appropriate.

3.8.2 Immunogenicity (IM) Analyses

Samples collected at predose on Days 1, 29, 85, 197, 323, and 449 and anytime on Day 631, including early termination and unscheduled samples for IM assessment will be analyzed for anti-ISIS 420915 antibodies (ADA). However, plasma samples collected at other time points (for PK

purposes) may also be potentially evaluated if deemed of further interest and warranted by the pharmacokinetic scientist. An evaluable sample will be designated 'IM positive' based on both positive screening and confirmation assay results (i.e., confirmed positive result), and otherwise will be deemed 'IM negative'. Sample IM results (screen positive/negative, confirmed positive/negative or unevaluable, and when applicable, titer of anti-ISIS 420915 antibodies) before, during, and after treatment with study drug (ISIS 420915 or placebo) (sample IM status) will be listed by treatment and dose.

Study subjects will be given 'IM positive' status if they have at least one confirmed positive sample result at any time during the treatment or post-treatment evaluation periods. Study subjects will be given 'IM negative' status if all evaluated IM sample results during the treatment and post-treatment evaluation periods are IM negative and they have at least one evaluable IM result collected post study drug treatment. Otherwise, a study patient will be given 'unknown' IM status. Subject IM results will be listed by treatment and dose for all evaluable patients, which will include but may not be limited to: subject IM status (positive, negative or unknown), the study day associated with the first positive IM status emerged (T_{first} , i.e., onset of ADA development), the last positive IM status observed (T_{last}), the time of last evaluable IM sample collected ($T_{\text{last sampling}}$), peak titer, and time to reach peak titer. The onset of ADA and time to reach peak titer will be calculated by:

- Onset in days = The date of first sample has "positive" sample IM status - first dose date +1;
- Time to reach peak titer in days = The date of first peak titer observed - first dose date +1;

Other immunogenicity data analysis (e.g. classification as transient or persistent status for IM positive subjects) if there is sufficient number of patients with transient IM status. Transient and Persistent ADA definitions are defined below and based on Shankar et al. (2014).

Transient ADA response will be defined as:

- Treatment-induced ADA detected only at one sampling time point during the treatment or follow-up observation period (excluding the last sampling time point, which will be considered persistent unless shown to be undetectable at a later time) or
- Treatment-induced ADA detected at two or more sampling time points during the treatment (including follow-up period if any), where the first and last ADA-positive samples (irrespective of any negative samples in between) are separated by a period less than 16 weeks, and the subject's last sampling time point is ADA-negative.

Persistent ADA response will be defined as:

- Treatment-induced ADA detected at two or more sampling time points during the treatment (including follow-up period if any), where the first and last ADA-positive samples (irrespective of any negative samples in between) are separated by a period of 16 weeks or longer or
- Treatment-induced ADA detected only at the last sampling time point of the study treatment period or at a sampling time point with less than 16 weeks before an ADA-negative last sample.

The sample IM incidence (number) and incidence rate (percent) at each evaluated study time point, and for the overall treatment and post-treatment evaluation period, as well as subject IM incidence and incidence rate, will be determined and appropriately summarized by treatment, as the total number of and percentage of evaluated subjects with IM negative, positive, and unknown status. Subjects with positive IM status may further be classified as transient or persistent status if applicable, and incidence and incidence rate for being transient or persistent will be appropriately summarized. Furthermore, onset, titer over time, and peak titer of the ADA response, if applicable, will be also appropriately summarized (using descriptive statistics) as median, quartiles (25% and 75%), and range and presented graphically, if deemed appropriate, by treatment at the discretion of the designated study pharmacokineticist and/or statistician (e.g., summarized at each evaluated study time point and overall; summarized by observed peak titer values from the individual IM positive subjects; etc.).

In addition to PK assessments (Section 3.8.1), selected efficacy (Sections 3.3 to 3.6) and safety (Section 3.8) assessments will also be further stratified by subject IM status (i.e., subject IM status being positive, negative or unknown) and presented in tables and/or graphically, as deemed appropriate or warranted by the designated study pharmacokineticist, medical monitor, and/or biostatistician. Other stratifications (e.g., based on antibody titer, onset of ADA, etc.) of selected PK, efficacy and safety assessments may also be performed if deemed warranted at the discretion of the pharmacokineticist, medical monitor, and/or biostatistician.

Efficacy measures to be stratified by subject IM status will include but may not be limited to TTR level, mNIS+7 and Norfolk QOL-DN score. Safety measures to be stratified by subject IM status will include but may not be limited to AEs, and lab tests for hematology and kidney functions.

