Appendix A Schedule of Procedures *Continued*
Post Treatment Evaluation Period

| | Post-Treatment Evaluation Period (6 Mo) ² | | | | | | | | Early Term |
|--|---|----------|----------|----------|----------|----------|----------|----------|------------|
| | W 67 | W 69 | W 71 | W 74 | W 77 | W 80 | W 83 | W 91 | |
| Study Week | 67 | 69 | 71 | 74 | 77 | 80 | 83 | 91 | |
| Study Day | D 463 | D 477 | D 491 | D 512 | D 533 | D 554 | D 575 | D 631 | |
| Visit Window (+/- Days) | 7 | 7 | 7 | 7 | 7 | 7 | 7 | 7 | |
| Informed Consent | | | | | | | | | |
| Inclusion/Exclusion | | | | | | | | | |
| Medical History | | | | | | | | | |
| Height | | | | | | | | | |
| HIV, Hepatitis B & C | | | | | | | | | |
| Biopsy for Amyloid ³ | | | | | | | | | |
| TTR Genotyping ³ | | | | | | | | | |
| Study Drug Admin. | | | | | | | | | |
| Physical Exam | | | | | | | | X | X |
| Vital Signs ^A (BP ⁴ , HR, RR, temp) | | | X | | X | | | X | X |
| ECG (12-Lead, triplicate) | | | | | | | | X | X |
| Pregnancy Test ⁵ | | | | | X | | | X | X |
| Chemistry Panel (Fasting) ^A | | | X | | X | | | X | X |
| Serum Creatinine (Fasting) | X | X | | X | | X | X | | |
| Hematology ^A | X | X | X | X | X | X | X | X | X |
| Weekly Platelet Monitoring ¹⁰ | Weekly Platelet Monitoring | | | | | | | | |
| Urinalysis ^A | | | | | | | | X | X |
| 24 hour Urine | | | | | | | | | |
| Thyroid Panel ^A | | | | | | | | X | X |
| Inflammatory Panel ^A | | | X | | | | | X | X |
| PT, aPTT, INR ^A | | | | | | | | X | X |
| Complement (C3) ^A | | | | | | | | | |
| Immunogenicity ^A | | | X | | | | | X | X |
| AE & Conmeds & Concomitant Procedures | | | X | | X | | | X | X |

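### SAP 3.8.2 leaves Day 491 off its antibody sample list, sets subject status and onset without reference to Day 1, and defines transient and persistent classes that overlap and leave a gap.

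*SAP*

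**What the plan says.** **Samples.** The SAP 3.8.2 list reads "Samples collected at predose on Days 1, 29, 85, 197, 323, and 449 and anytime on Day 631", and the sentence goes on "including early termination and unscheduled samples for IM assessment will be analyzed" for anti-drug antibodies (ADA). Plasma drawn at other times for PK "may also be potentially evaluated if deemed of further interest and warranted by the pharmacokinetic scientist". In the post-treatment part of Protocol Appendix A the row reads "Immunogenicity ^A | | | X | | | | | X | X". Its marks fall under Week 71 (Day 491), Week 91 (Day 631) and early termination.

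**Subject status and onset.** A subject is IM positive "if they have at least one confirmed positive sample result at any time during the treatment or post-treatment evaluation periods". Onset is the date of the first positive sample minus the first dose date, plus one. Day 1 is assayed, and results from before treatment are listed. SAP 3.2.1.4 limits the immunogenicity summary tables to post-baseline data.

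**Classes.** A response is transient if it is "Treatment-induced ADA detected only at one sampling time point during the treatment or follow-up observation period", where a positive at the last time point is held to be persistent unless a later sample is negative. It is also transient with two or more positives whose first and last are under 16 weeks apart, if the last sample is negative. It is persistent with two or more positives spanning 16 weeks or longer. It is also persistent if it is "Treatment-induced ADA detected only at the last sampling time point of the study treatment period", or at a time point under 16 weeks before a negative last sample. The split is made only if enough patients are transient.

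**The concern.** Under SAP 3.8.1 and 3.8.2, subject IM status stratifies the PK results and selected efficacy and safety results, including TTR, mNIS+7, Norfolk QOL-DN, adverse events, and hematology and kidney tests. These tables ask whether an antibody response to the drug goes with lower exposure, weaker effect or more toxicity. If the positive stratum mixes reactivity present before the first dose with a response to treatment, any such contrast is blurred, and incidence is raised in the placebo arm as well. If a scheduled off-drug sample is not assayed, a late response can be missed. If one patient meets both sub-classes and another meets neither, those counts depend on the programmer's choice.

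**Working it through.** The plan states no figure on this point to reproduce. The check compares the sections and applies the rules literally.

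**1. Day 491.** With week = (day − 1)/7 + 1:

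- Day 449 is Week 65, Day 491 is Week 71 and Day 631 is Week 91.
- Intervals: 491 − 449 = 42 days (6 weeks); 631 − 491 = 140 days (20 weeks); 631 − 449 = 182 days (26 weeks).
- Day 491 is in Appendix A and not in the SAP 3.8.2 list. SAP 3.8.1.2 does name Day 491 as a scheduled collection for the half-life.
- A patient negative at every listed day and positive only at Day 491 is therefore IM negative if only the listed samples are run.

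**2. Day 1.** Take a patient positive at Day 1 before dosing and positive at Day 29 with the same titer.

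- Status: one confirmed positive during treatment makes the subject IM positive. Day 1 does not enter the rule.
- Onset: if Day 1 pre-dose is not counted as within the treatment period, onset is 29 − 1 + 1 = Day 29. If it is counted, onset is 1 − 1 + 1 = Day 1. Either way, reactivity that preceded the drug is reported as onset of ADA development.
- The post-baseline limit in SAP 3.2.1.4 does not remove this patient, because the Day 29 result is post-baseline.
- The transient and persistent rules apply to treatment-induced ADA. With no definition of that term, it cannot be said whether they cover this patient.

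**3. Transient and persistent.** Taking 16 weeks as 112 days, the clauses were applied to every pattern with at least one positive after Day 1 (2^k − 1 patterns for k samples):

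| Samples after Day 1 | Patterns | Persistent only | Transient only | Both | Neither |
|---|---|---|---|---|---|
| SAP list to Day 631 | 63 | 57 | 5 | 1 | 0 |
| SAP list plus Day 491 | 127 | 119 | 7 | 1 | 0 |
| Ending at Day 449 (open-label extension) | 31 | 26 | 5 | 0 | 0 |
| Ending at Day 491 | 63 | 56 | 5 | 1 | 1 |

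These are counts of possible patterns, not probabilities. In each row with an overlap, the pattern meeting both classes is positive only at Day 449 with a later negative. Adding Day 491 does not cure it. The pattern meeting neither is positive at Days 449 and 491 (42 days apart) with Day 491 last.

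Early exits add further cases:

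- Positive only at Day 29, with Day 85 the last sample and negative: one time point that is not the last, so transient; 85 − 29 = 56 days (8 weeks) before a negative last sample, so also persistent.
- Positive at Days 29 and 85, with no later sample: 56 days apart, so the 16-week persistent clause fails; last sample positive, so not transient; more than one positive, so the single-time-point clauses fail. Neither class applies.

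**The case against.** **Day 491 may be covered elsewhere.** SAP 3.2.1.3 bases its post-treatment windows on the scheduled assessments, and the immunogenicity rows are redacted, so a Day 491 window may exist. PK plasma is drawn from all follow-up patients that day, and 3.8.2 allows it to be tested. This stands in part. But a window only places a result that exists, and the discretionary clause turns a protocol-scheduled immunogenicity sample into a case-by-case choice. Patients entering the open-label extension have no Day 491 visit, so only those in post-treatment follow-up are affected.

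**Day 1 is not ignored.** This is right. It is assayed, it is listed, and the term treatment-induced implies a baseline comparison. What remains is that subject status and onset do not use Day 1 and the term has no definition.

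**The overlap resolves itself.** The exception in the first transient clause can be read as making positive at Day 449, negative at Day 631 transient. The persistent clause on the last treatment-period sample carries no such exception, so both apply as written. Nor does the early-termination sample close the gap: a patient positive at Day 85 and again at a last, early-termination sample under 16 weeks later meets neither class.

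**Little depends on it.** No primary or secondary test, alpha or stopping rule uses IM status, and the stratified efficacy and safety outputs are produced as judged appropriate. That stands, and it limits the weight of the point.

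**Conclusion.** The three rule faults are real and should be corrected. The first two can change subject incidence and the IM-stratified tables. Against the planned 90 active and 45 placebo patients, one misplaced patient is 1/90 = 1.1 or 1/45 = 2.2 percentage points. The documents give no ADA rate and no rate of pre-existing reactivity, so the total cannot be sized. Purely as illustration, if 1–10% had pre-existing reactivity (an assumption) and all tested positive again after baseline, that would be 0.9–9 active and 0.45–4.5 placebo patients.

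Three stronger readings are tempting and not supported:

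- A reader might infer that all three faults misclassify incidence and the strata. The transient/persistent fault cannot: incidence and strata use positive, negative and unknown, and the split is an optional further step.
- A reader might infer that every late single positive falls under conflicting clauses. Positive only at Day 323 with Day 449 negative and last is 126 days (18 weeks) before that negative, so it is transient only. Positive only at Day 631 is persistent only.
- A reader might quote a percentage over-count of ADA. That needs a second assumed rate, for treatment-induced cases, which the documents also lack.

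**What to change.** In SAP 3.8.2, before unblinding:

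1. Add Day 491 to the samples to be analysed, to match Appendix A.
2. Define treatment-emergent ADA against Day 1: Day 1 negative followed by a confirmed positive, or Day 1 positive with a titer rise of a fold fixed before unblinding. Use this for subject status and onset. Report pre-existing positives without such a rise as a separate row.
3. Add a precedence rule so that every treatment-emergent positive patient is in exactly one class. One rule that works: transient if the first and last positives are under 16 weeks apart and the last sample is negative and at least 16 weeks after the last positive; persistent otherwise. The 63 patterns on the SAP list then split 57 persistent and 6 transient, and the 127 with Day 491 split 119 and 8, with none in both or neither.

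The cost is SAP wording, derivation code and assay runs for Day 491. The Day 1 and Day 491 samples are already scheduled. The headline ADA rate may come out slightly lower.
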